3.5 Interim Analyses

No interim analysis is planned.

However, the database will be locked after all patients have completed their Week 12 Visit and main objectives analysis will be performed on unmasked data. A Blind Data Review Meeting will take place after the last enrolled patient completes Week 12 Visit and before unmasking of the study

[figure not shown]
At the end of the study (i.e. after all patients have completed Week 32 Visit), an updated analysis will be performed presenting the complete study data.

Further details on the two distinguished analyses are provided in section 9 of this SAP.

3.6 Changes in the Conduct of Study or Planned Analysis compared to Protocol

The following changes of the study conduct did affect the planned analysis:

- Mitochondrial Redox potential: during the set-up process of the eCRF, test type and Index number were identified as endpoints to evaluate MRP. However, it was not possible at the site to identify an index number for each patient for data entry to the eCRF. In July 2017, it was decided by the sponsor, that no data will be entered on the eCRF and reporting of MRP assessments will be performed separately by the investigator.

- Changes in ERG including pattern ERG: during the set-up process of the eCRF, it was planned to assess the following data from performed ERG into the eCRF: Result (Normal/Abnormal), Amplitude A1-B1 Photopic 3.0 (0.5 Hz), Latency ISO-B1 Photopic 3.0 (0.5 Hz), Amplitude ISO-B1 Scotopic 0.01 (0.5 Hz), Latency ISO-B1 Scotopic 0.01 (0.5 Hz), Amplitude ISO-B1 Photopic 3.0 Flicker 30Hz, Latency ISO-B1 Photopic 3.0 Flicker 30 Hz, Amplitude N1-P1 wave oscillatory potential (1 Hz), Latency N1-P1 wave oscillatory potential (1 Hz).

In July 2017, based on investigator’s proposal, it was decided to use photopic negative response number (phNR) as a more relevant measure of assessing ERG changes (Kim, Park, Ohn, 2010), which will be chosen for analysis and be recorded on the eCRF alternatively.

- Humphrey Visual Field assessment (HVF): it was recognized at site, that for patients with low vision, HVF assessment could not be performed according to SITA-Standard. For these patients the FASTPAC standard will be applied (see protocol clarification letter as of 04AUG2017). The output for these assessments differ from SITA standard by not providing information on mean deviation, standard deviation and visual field index. The eCRF was changed to enable a proper statistical evaluation by adding applied algorithm (SITA/FASTPAC) and a qualitative evaluation of the change in visual fields (pre-treatment assessment/improved/no change/worsened, not assessable) to enable a statistical evaluation of secondary endpoint “Change in HVF”. However, completion of this qualitative assessment was refused by the investigator. According to sponsor’s decision on 17NOV2017, results of HVF assessments will not be analysed but listed only.

This does not affect the evaluation of primary outcome “Unexpected severe progression of optic neuropathy measured on HVF or optic nerve examination”.

The following refinements of the pre-planned analysis in the study protocol were implemented in this SAP:

- The study protocol defines the Safety Set as all treated patients. However, the Safety Set will serve a primary analysis cohort for the primary study objectives. To ensure formal maintenance of randomization, the Safety Set will be refined to “all randomized patients who received at least one study treatment”. It is notable, that randomization and dispensation of first study medication are both performed at site within one process. So, it is not expected that a patient would be treated without being randomized.
- Study protocol section 11.5.4 provides specifications of tables and listings for displaying documented AEs. This presentation of data will be aligned to data presentation of other studies investigating rhNGF to facilitate data interpretation. This change is purely organizational without omitting any data presentation described in the study protocol with one exception: due to the relative few numbers of patients, no separate listing of concomitant disease and medications will be provided for patients with adverse events.

4 General Definitions

4.1 Report Language

The TLFs as output of the analyses will be prepared in English.

4.2 Analysis Software

The statistical analysis will be performed using the SAS[®] statistical software package (Statistical Analysis System, Version 9.3 or later).

5 Data Preparation

5.1 Data Handling and Medical Coding

For data quality control and medical coding, please refer to the Data Management Plan, including the Data Validation Plan in its most recent version.

5.2 CDISC

[figure not shown]
All output as defined in the SAP will be generated based on CDISC ADaM datasets following ADaM implementation Guide 1.0, as per contract with Dompé farmaceutici S.p.A. SDTM programming will follow SDTM version 1.3 together with SDTM implementation guide 3.1.3.

Specifications for the ADaM datasets (as well as SDTM datasets) are described in a separate document.

5.3 SAS-Programming Quality Level

The following quality level of programming deliverables will be applied, as per contract with Dompé Farmaceutici S.p.A. All statistical output will receive a tailored Quality Control (QC) approach by:

- Full independently double programmed reproduction of CDISC:
 - o SDTM datasets
 - o ADaM datasets
- Full independently double programmed reproduction of results of
 - o Primary endpoint analysis and its underlying analysis dataset(s) and table(s),
 - o Randomization merging
 - o Analysis population merging, and
 - o Visit windows programming
- Listings will not be double programmed.
- All other tables will be given a reduced QC involving independent reproduction (i.e. double programming or manual cross checking a subset of patients) of approximately 20% of the summary results (selection to be agreed upon with the sponsor).
- All tables and listings will undergo comparison with specification (i.e. SAP and templates), cross checking with other tables and listings, a sensibility review and SAS-log review.

6 Analysis Sets and Subgroups

6.1 Analysis Sets

Evaluability for all patients and visits will be determined during a Blind Data Review Meeting, which will take place before unmasking the study for the main objective analysis (i.e. comprising data up to Week 12 Visit).

The Total Set (TOT) will include all patients that have signed informed consent.

The Intent-to-treat Set (ITT) will include all randomized patients and will be used for all exploratory efficacy analyses. All analyses based on the ITT will be summarized by the treatment randomized.

The Safety Set (SAF) will include all randomized patients who receive at least one dose of study medication. This safety population will be used in the analysis of all safety endpoints.

A subset of all patients in the SAF, who entered the Follow-Up Period (SAF-F), will be used in addition to present event-type analyses of the Follow-Up Period. A patient will therefore be considered as entering the Follow-Up Period, if he/she did not terminated the study at or before the Week 8 visit.

All analyses based on the SAF and SAF-F will be summarized by the treatment received.

For the study, both eyes are under investigation. For each patient, a Primary (Study) Eye and a corresponding Secondary Eye will be defined during a Blind Data Review Meeting (BDRM) to enable a patient based presentation of statistical analyses.

For each patient, an eye will be considered as Primary Eye, if

- the eye was treated and
- the investigator considered this eye as qualifying eye.

If both eyes are considered as qualifying eye, the right eye will be chosen.

The other eye will then be considered as Secondary Eye, if the eye was treated. If the other eye was not treated with study medication, no Secondary Eye will be assigned for this patient.

6.2 Subgroup Definitions

For the presentation of adverse events by age, age categories ' ≤ 65 years' and '>65 years' will be applied.

7 Definition of Time Points and Analysis Variables

7.1 Definition of Time Points

The study consists of 7 scheduled clinical evaluation visits: Screening Visit, Baseline Visit (Therapy Initiation), Week 1, Week 4, Week 8, Week 12 and Week 32 Visit. Week 1 Visit has a window of ± 2 days, Week 4 Visit has a window of ± 4 days, while Week 8, 12, 32 Visits have a window of ± 7 days, at the discretion of the investigator, required procedures for a scheduled visit may be performed over 2 consecutive days.

If a patient returns to the clinic prior to their next scheduled study visit for assessment of an adverse event, an Unscheduled Visit should be conducted. Procedures conducted at the Unscheduled Visit are at the discretion of the Investigator.

Any patient who exits early from the study must undergo all procedures outlined at Week 8 Visit if the discontinuation occurs at or before Week 8 Visit.

All assessments except event type data will be analysed according to the nominal Visit identifier on the CRF page, irrespective of meeting the time window as specified in the study plan and of having the procedures performed over 1 or 2 consecutive days.

This rule does not hold for patients, who terminate study during treatment. For these patients, the visit needs to be shifted to Week 1, Week 4 or Week 8 visit depending on the visit window specified below.

Unscheduled visits will not be considered for by-visit analyses but all collected data will be listed. Documented unscheduled visits will be labelled as “Unscheduled Visit x.01”, “Unscheduled Visit x.02”, “Unscheduled Visit y.01” etc. indicating the number of the last preceding visit plus a consecutive sequence number.

The Baseline value is generally defined as the last non-missing measurement collected or derived prior to the first Study Treatment Administration as recorded on eCRF page “Administration of Study Drug’ in variables Date/Time of Application of First Dose.

The Treatment Day of an event/assessment will be calculated relative to the First Study Treatment [defined as Variable “Date of First Dose Treatment’, recorded on “Study Drug Dosing Dates’ eCRF form].

The Treatment Day of events/assessments occurring before the First Study Treatment will be calculated as:

- Treatment Day = (Date of assessment/event - Date of First Study Treatment).

For events/assessments occurring on or after First Study Treatment Administration, Treatment Day will be calculated as:

- Treatment Day = (Date of assessment/event - Date of First Study Treatment) + 1.

Table 2: Study Visits

Scheduled Visit	Scheduled Visit Label	Scheduled Study Day	Visit Window
Screening Visit	Screening	Before Baseline Visit	Up to 4 weeks before date of Baseline Visit
Baseline Visit Day 0	Baseline	0	Date of Baseline Visit – Date of First Study Treatment in [-1, 0]
Week 1	Week 1	7	Visit date – Date of First Study Treatment in [5 – 9]
Week 4	Week 4	28	Visit date – Date of First Study Treatment in [24 – 32]
Week 8	Week 8	56	Visit date – Date of First Study Treatment in [49 – 63]
Follow-up Visit Week 12	Week 12	84	Visit date – Date of First Study Treatment in [77 – 91]
Follow-up Visit Week 32	Week 32	224	Visit date – Date of First Study Treatment in [217 – 231]
Documented unscheduled Visits will be labeled as “Unscheduled Visit x.01”, “Unscheduled Visit x.02”, “Unscheduled Visit y.01”... .			
Date of First Study Treatment is to be taken from eCRF page “Study Drug Dosing Dates”.			

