10.4. UNSCHEDULED VISITS

If a subject returns to the clinic prior to their next scheduled study visit for assessment of an adverse event, an Unscheduled Visit should be conducted. Procedures conducted at the Unscheduled Visit are at the discretion of the Investigator and may be among the study procedures or additional procedures not performed during the study but deemed necessary by the investigator. The clinical information obtained during any unscheduled visit is to be recorded in the electronic Case Report Forms. If the patient is discontinued at the unscheduled visit, the eCRFs for the Week 8 visit should be completed if the withdrawal occurs at Week 8; for all other patients the Early Exit Visit should be completed.

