11.5.4. Safety Analysis

Safety variables will be presented for the Safety population.

The primary safety endpoint in this study is Adverse Events (AEs). AEs will be recorded at the scheduled study visits and may also be recorded at any unscheduled visit that occurs during the study.

AEs will be presented, by treatment group, in terms of the incidence, severity and relationship to the study drug, overall and by SOC (System Organ Class) and preferred term. Serious AEs (SAEs) will be presented in the same way. All adverse events will be reported by MedDRA preferred term.

The following adverse event summary tables and listings will be provided:

Tables:

- Frequency and Incidence of Subjects with Adverse Events
- Frequency and Incidence of Subjects Discontinued Due to Adverse Events
- Frequency and Incidence of Subjects with Serious Adverse Events
- Adverse Events by Coded Adverse Event and SOC
- Overall Frequency and Incidence of Adverse Events
- Overall Frequency and Incidence of Adverse Events by Severity
- Overall Frequency and Incidence of Treatment-Related Adverse Events
- Overall Frequency and Incidence of Adverse Events Occurring at Rates Greater Than or Equal to 1.0%
- Overall Frequency and Incidence of Adverse Events by Age

Listings:

- Concomitant Diseases and Medications for Subjects with Adverse Events by Investigator and by Subject
- Coded and Descriptive Terms of Adverse Events by Investigator and by Subject
- Deaths, Other Serious or Clinically Significant Adverse Events
- Adverse Events by Investigator and by Subject

In addition to reporting of adverse events for any untoward (unfavorable and unintended) medical occurrences, adverse events will also be reported for any clinically relevant change from baseline in any assessment evaluated during the study, based upon an assessment by the Investigator.

Ocular tolerability as measured by the VAS will be analyzed by means of analysis of variance, including terms for treatment, time, and treatment by time interaction.

Best corrected distance visual acuity, external ocular examination, slit lamp examination, intraocular pressure, and dilated fundus ophthalmoscopy, will be presented with the appropriate descriptive statistics and shift tables will be used to present shifts from before and after treatment at each recording time points.

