10.8.4 External Ocular Examination

All evaluations of the motility of extraocular muscle Right and Up, Right, Right and Down, Left and Up, Left, Left and Down will be summarized descriptively by treatment group and study visit for the Primary Eye as well as the Secondary Eye. This analysis will be performed on the SAF. In addition, a shift table will be provided displaying the status of all scheduled Post-Baseline Visits in relation to the Baseline status. The percentages are based on the number of SAF patients in the respective baseline stratum of considered treatment group. These data will also be listed.

[figure not shown]
Incidences of proven eyelid deformity/abnormality, abnormal motor function of eyelids, corneal exposure in case of closed eyelid, proven punctal occlusion, punctal plugs, thermal or surgical occlusion or other punctal occlusion will be presented by treatment group and study visit for the Primary Eye as well as for the Secondary Eye. In addition, a shift table (Presence, Absence of considered abnormality) will be provided displaying the status of all scheduled Post-Baseline visits in relation to the Baseline status.

Incidences will be calculated as number and percentages of affected patients in respective treatment groups of the SAF. The percentages in the shift tables are based on the number of SAF patients in the respective baseline stratum of considered treatment group. The analysis will be performed on the SAF. Moreover, these data will be listed.

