10.8.5 Slit Lamp Examination

All grading assessments of different eye structure (excluding assessment for other structures) will be summarized descriptively by treatment group and study visit for the Primary Eye as well as the Secondary Eye. In addition, a shift table will be provided displaying the status of all scheduled post-baseline visits in relation to the baseline status. The percentages are based on the number of SAF patients in the respective baseline stratum of considered treatment group. These analyses will be performed on the SAF.

All data recorded on the eCRF page 'Slit Lamp Examination (Biomicroscopy)' will be listed for the SAF.

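### Slit-lamp, fundus and external-examination grades recorded only at an unscheduled visit are listed but enter no by-arm table

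*SAP*

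**What the plan says.** SAP section 7.1 ties unscheduled visits to adverse events, as protocol section 10.4 does, and leaves their content open: "Procedures conducted at the Unscheduled Visit are at the discretion of the Investigator". It then sets the analysis rule: "Unscheduled visits will not be considered for by-visit analyses but all collected data will be listed".

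For slit-lamp findings, SAP section 10.8.5 plans a descriptive summary by arm and study visit, and in addition "a shift table will be provided displaying the status of all scheduled post-baseline visits in relation to the baseline status". Section 10.8.7 (fundus) uses the same wording. Section 10.8.4 (external examination) says "a shift table will be provided displaying the status of all scheduled Post-Baseline Visits in relation to the Baseline status". The table list in SAP section 12 has a summary and a shift table for each of these examinations, and nothing based on the worst value or on any time point.

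Protocol section 11.5.4 says of these examinations that "shift tables will be used to present shifts from before and after treatment at each recording time points". The same section says "adverse events will also be reported for any clinically relevant change from baseline in any assessment evaluated during the study", on the investigator's assessment.

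Two other safety outcomes do use unscheduled data. SAP section 7.2.7 counts unscheduled visits for unexpected severe progression of optic neuropathy (USPON) from acuity, ERG and OCT. Section 7.2.9 counts scheduled and unscheduled assessments for substantial worsening of visual acuity.

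**The concern.** Safety and tolerability are the primary objective, and graded examinations are the structured, objective part of the ocular safety data. An unscheduled visit exists because something went wrong, so an examination done there is more likely than a routine one to record an abnormal grade. If the patient has recovered by the next scheduled visit, the tables show no change for that eye, and the abnormal grade can be found only by reading a listing. With 40 patients on rhNGF and 20 on vehicle, a few such grades could alter the displayed picture.

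**Working it through.** The plan gives no figure on this point, so there is none to reproduce. The check traces where a grade goes, then illustrates how sparse the scheduled examinations are.

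**1. Tracing a grade recorded only at an unscheduled visit**

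| Output | Unscheduled data counted? | Source |
|---|---|---|
| External, slit-lamp and fundus summaries | No | SAP 7.1, 10.8.4, 10.8.5, 10.8.7 |
| External, slit-lamp and fundus shift tables | No, scheduled visits only | same sections |
| Listings of these examinations | Yes | SAP 7.1 |
| USPON | Yes | SAP 7.2.7 |
| Substantial worsening of visual acuity | Yes | SAP 7.2.9 |
| Adverse event tables | Yes, not tied to a visit | SAP 10.8.1.2 |

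The adverse event tables carry the term, relatedness and severity by arm. Protocol section 12.3.2 grades severity by interference with the patient's usual function. The slit-lamp scale in SAP section 7.2.11 grades what the examiner sees, such as the intensity of the Tyndall effect. The two scales need not agree, so the first does not stand in for the second.

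**2. The early-exit route**

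SAP section 7.1 moves the visit of a patient who terminates during treatment to Week 1, 4 or 8 by window. The windows in SAP Table 2 are days 5-9, 24-32 and 49-63:

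- days covered: 5 + 9 + 15 = 29 of the 64 days from 0 to 63;
- days not covered: 64 - 29 = 35, and 35/64 = 55%.

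An exit on an uncovered day has no stated destination. A patient who recovers and stays in the study does not use this route at all.

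**3. Illustration of scheduled coverage**

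Inputs: on-treatment slit-lamp and external examinations at nominal days 7, 28 and 56, and fundus examination at day 56 only (protocol section 2). Assumptions, not in the documents: one episode per eye, onset uniform over 56 days, duration *d* days. A scheduled examination at day *v* coincides with the finding if onset falls in the *d* days up to *v*. For day 7 this interval cannot exceed 7 days.

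| *d* | Slit lamp or external | Fundus |
|---|---|---|
| 5 | (5 + 5 + 5)/56 = 15/56 = 26.8% | 5/56 = 8.9% |
| 7 | (7 + 7 + 7)/56 = 21/56 = 37.5% | 7/56 = 12.5% |
| 10 | (7 + 10 + 10)/56 = 27/56 = 48.2% | 10/56 = 17.9% |

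A count by whole days (57 onset days, 0 to 56) gives slit-lamp coverage of 3/57 = 5% at 1 day, 21/57 = 37% at 7 days, 36/57 = 63% at 14 days and 50/57 = 88% at 21 days. The answer therefore depends heavily on the assumed duration. In follow-up the gap is wider: no examination is scheduled between Week 12 and Week 32.

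**4. Weight of one patient**

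1/40 = 2.5% of the rhNGF arm; 1/20 = 5% of the vehicle arm.

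**The case against.** The strongest reply is that the event is not lost. The visit is held for an adverse event, which is tabulated by arm whatever the visit. Clinically relevant examination changes are to be reported as adverse events, and the highest severity of each episode is recorded. Severe intraocular inflammation is an event of special interest and by default serious (protocol section 12.1.6), so it also has by-arm outputs. This stands. A reader might infer that the worst findings drop out of the safety comparison altogether; they do not. Only the examination grade is missing from it.

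A reader might also infer that the rule favours rhNGF. The documents do not support that. The rule applies to both arms, and nothing shows more unscheduled visits on active treatment. The transient reactions in protocol section 4 are symptoms after instillation, and for the healthy-volunteer study that section reports no clinically significant examination changes.

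Nor can the complement of the slit-lamp coverage, 52-73%, be read as data removed by the rule. Examinations at these visits are discretionary, and a finding that prompts no visit is missed with or without the rule.

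Finally, USPON and acuity worsening are incidences over a period, whereas shift tables are by-visit displays, so the difference in handling is not a direct contradiction. The protocol's phrase on recording time points does not clearly include unscheduled visits, so a departure from the protocol is not established. Both points are fair. They do not explain why no period-based summary is planned for these three examinations.

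**Conclusion.** The gap is real but narrow. Grades recorded only at an unscheduled visit are compared between arms in no table for three safety examinations, although the SAP uses such data for two other safety outcomes. The adverse event tables cover the event but not the grade, and early exit gives only a partial route into the examination tables. How many grades are affected depends on how often examinations are done at unscheduled visits, which the documents do not say. The 27-48% and 9-18% rest on assumed onset and duration, and describe scheduled coverage only. These tables are descriptive, so no test or error rate is affected. Severity is minor; the change is worth making because it is cheap.

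**What to change.** Keep the by-visit rows. In SAP sections 7.1, 10.8.4, 10.8.5 and 10.8.7, add to Tables 14.3.3-1.2, 14.3.3-2.2, 14.3.4-1.2 and 14.3.6-1.2 a supplementary shift row for the worst post-baseline grade, scheduled or unscheduled. Give one row for the treatment period (after first dose, up to and including Week 8) and one for follow-up.

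The derivation needs three short rules:
- For normal/abnormal or present/absent items, the worst grade is any abnormal finding.
- Not-done or not-evaluable codes count as missing. The lens category for cataract extraction is not treated as the top of the opacity scale.
- At the main objective analysis the follow-up row stops at Week 12, as SAP section 9.1 does for visit-based tables.

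Footnote each row with the number of patients and of unscheduled examinations per arm.

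The cost is one derived record per eye, structure and period, and two rows per table, from data already collected. The downside is that patients with more visits have more chances of a worse grade. The footnote shows that imbalance but does not remove it, so the row should be labelled supplementary.
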